6.3.3.4 Stool Sample Storage and Transport

Immediately after collecting their infant's stool swab and chunk samples, parents will store the whole chunk sample (tube with brown cap) in their home freezer within the study-provided freezer bag. Parents will bring the freezer bag containing the collected stool chunk samples on a provided frozen ice pack to the in-person Study Visit on Day 7 and the in-person Study Visit on Day 28.

Stool swab samples (tubes with white cap) should be stored at room temperature. Parents will bring the collected stool swab samples with them to the in-person Study Visit on Day 7 and the in-person Study Visit on Day 28.

Hemoccult cards should be stored at room temperature. Parents will bring the completed hemoccult cards with them to the Study Visits on day 7 and day 28.

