3.1.2. Secondary Endpoints

- The percentage of patients testing negative for blood in stool by Study Day 7, 14 and 28 by hemoccult testing
- The percentage of patients with no gross/visible blood in stool by Study Day 7, 14 and 28 by parental report
- Changes to stool frequency by Study Day 7, 14 and 28
- Changes to clinical symptoms including GER, feeding difficulties, sleep disturbance and poor growth
- The occurrence of supplement-related adverse events

3.1.3 Biomarkers / Exploratory Endpoints:

- Fecal calprotectin levels
- Fecal pH levels
- Fecal metabolomics
- Markers of inflammation and enteric cytokines including, but not limited to, IL-1, IL-8 and TNF-alpha in stool
- Levels of eosinophil-related granular proteins in stool
- Intestinal permeability/integrity markers including, but not limited to, lipocalin (NGAL)

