6.3.1.2 Secondary Objectives

The secondary objectives of this study are to evaluate: clinical symptoms including blood in stool, stool frequency, GER, feeding difficulties, sleep disturbance and poor growth

6.3.1.2.1 Blood in stool Blood in stool will be assessed by daily hemoccult stool test on Days 0, 1-14, 21 (+/- 1 day), 28 (+/- 1 day)

6.3.1.2.2 Stooling Infant stooling will be assessed by daily log capturing frequency, consistency, night stooling, and presence of mucus or gross blood

6.3.1.2.3 Infant GER Infant GER will be assessed by standard Reflux Questionnaire on Day 7, 14, 21, and 28

6.3.1.2.4 Infant Sleep Infant sleep duration/quality will be assessed by Questionnaire on Day 7, 14, 21, and 28

6.3.1.2.5 Infant Feeding Infant feeding difficulties will be assessed by Questionnaire on Day 7, 14, 21, and 28

6.3.1.2.6 Infant Growth Infant growth will be monitored at weekly visits by measuring weight, length, and head circumference

6.3.1.2.7 Adverse Events Supplement-related adverse events will be recorded by parents in a health log, in consultation with the study team and PI.

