6.3.3 Stool Sample Documentation, Training, Storage, and Handling

6.3.3.1 Baseline Samples

Baseline stool swabs and chunks of stool must be collected before the first study supplementation is consumed. After collection, the parents will store the swab tubes (white top tube) at room temperature and will store the chunk tubes (brown top tube) in their home freezer in a bag provided to retain those samples. At the Day 7 in-person Study Visit, parents will bring all Days 0-7 stool samples (swab, chunk, and card) with them to the visit. At the end of the study, parents will bring all remaining stool samples to the study site at the Day 28 End of Study in-person Visit. All efforts should be made to collect stool samples within the target collection windows. Parents will be trained on how to collect the samples at enrollment and as needed throughout the study.

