9. STATISTICAL ANALYSIS

9.1 SAMPLE SIZE CALCULATIONS AND STATISTICAL ANALYSIS PLAN

9.1.1 Determination of Sample Size

Approximately 100 infants and 100 mothers will be recruited and screened for the study to obtain a sample size of 50 participants for randomization, assuming a 50 percent screen fail rate. Forty (40) participants are expected to complete the study assuming a 20 percent drop-out rate. This sample size is based on a literature review of randomized clinical trials and the anticipated changes to the microbiome based on previous studies of *B. infantis*.

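### Cards and stool from Days 8-14 reach the site only at Day 28, although a Day 14 visit is scheduled; adding a Day 14 hand-over would protect that time point at almost no cost

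*Combined protocol and SAP*

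**What the plan says.** Section 6.3.3.1 splits the hand-over in two. At Day 7, "parents will bring all Days 0-7 stool samples (swab, chunk, and card) with them to the visit". After that, "parents will bring all remaining stool samples to the study site at the Day 28 End of Study in-person Visit". Section 6.3.3.4 repeats the two days for frozen tubes and swabs, and for the cards: "Parents will bring the completed hemoccult cards with them to the Study Visits on day 7 and day 28". On card storage it says only this: "Hemoccult cards should be stored at room temperature". The stool-to-site row of Table 1 (6.4) is marked at Day 7 and Day 28 and nowhere else, so text and table agree.

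Table 1 also marks Day 14 for a study visit, a physical exam, the clinician symptom tool, stool collection and a hemoccult test.

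Day 14 is a named analysis point. Section 3.1.2 lists as a secondary endpoint: "The percentage of patients testing negative for blood in stool by Study Day 7, 14 and 28 by hemoccult testing". Section 6.6.3 lists Day 14 as a stool sampling day for sequencing.

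On attrition, 9.1.1 says: "Forty (40) participants are expected to complete the study assuming a 20 percent drop-out rate". Section 9.2.2 rules out imputation. Section 10.1.3 provides safety follow-up after early termination and does not mention collecting outstanding cards or samples.

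**The concern.** The family appears to be at the site on Day 14, at the end of supplementation, but the second week's cards and stool stay at home for two more weeks. Two things follow.

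- **Avoidable loss.** An infant can attend Day 14, leave before Day 28, and contribute no Day 14 card, swab or frozen tube. With no imputation, that infant drops out of the Day 14 hemoccult proportion and the Day 14 microbiome data.
- **Unequal handling.** Of the three hemoccult endpoint days, the middle one has a long room-temperature wait before hand-over and the other two have none. If cards are developed on receipt, any effect of storage would fall on Day 14 and not on the days it is compared with.

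**Working it through.** **Inputs.** Return days are 7 and 28 (6.3.3.1, 6.3.3.4, Table 1). Hemoccult days are 0, 1-14, 21 and 28 (6.3.1.2). The plan screens 100 infants with 50% screen failure and 20% drop-out (9.1.1). It does not give the timing of drop-out.

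**The plan's own figure.** 100 × (1 − 0.50) = 50 randomized, and 50 × (1 − 0.20) = 40 completers. This reproduces, and it implies 50 − 40 = 10 drop-outs.

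**Wait before hand-over** = return day − collection day.

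| Collected | Returned | Wait (days) |
|---|---|---|
| Day 0 | Day 7 | 7 |
| Days 1-7 | Day 7 | 6 down to 0 |
| Day 8 | Day 28 | 20 |
| Day 14 | Day 28 | 14 |
| Day 21 | Day 28 | 7 |
| Day 28 | Day 28 | 0 |

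Days 8-14 therefore wait 14 to 20 days, or 13 to 21 if the last visit moves by one day either way. The three endpoint cards wait 0, 14 and 0 days.

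**Infants at risk at Day 14.** Let f be the share of the 10 drop-outs who leave after Day 14, and assume that a family that leaves returns nothing. Then 40 + 10f infants are still in the study at Day 14, 40 return material at Day 28, and 10f are at risk.

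| f | In study at Day 14 | At risk | Share |
|---|---|---|---|
| 0 | 40 | 0 | 0% |
| 0.25 | 42.5 | 2.5 | 5.9% |
| 0.5 | 45 | 5 | 11.1% |
| 0.75 | 47.5 | 7.5 | 15.8% |
| 1 | 50 | 10 | 20% |

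Even drop-out over 28 days gives 10 × 14/28 = 5, the middle row.

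**With a Day 14 hand-over.** The wait for Days 8-14 becomes 14 − 8 = 6 down to 14 − 14 = 0 days, the same as for Days 1-7. Day 14 material in hand becomes 40 + 10f instead of 40: 45 if half of the drop-outs leave after Day 14, and 50 if all do.

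**Which material is involved.** Hemoccult testing is marked in Table 1 throughout Days 8-14. For stool the plan differs by section. Sections 6.3.2.1 and 6.4.1 have daily collection through Day 14. Table 1 marks Day 14 but not Days 8-13, and 6.6.3 lists only Day 14 in that span. The Day 14 sample is common to all of them.

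**The case against.** The text and Table 1 agree, so this is a design choice and not an error, and several stronger readings do not stand.

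A reader might infer that Day 14 results are lost whenever a family leaves later. The plan does not bar a withdrawn family from returning material; it only lacks a step for asking. The exposure is also limited to cards and stool. The Day 14 exam and symptom tool are done at the visit, and visible blood comes from the parents' stooling log, which is not part of this hand-over. The primary comparison runs from Baseline to Day 28 (9.2.3), so an infant who leaves before Day 28 lacks it in any case.

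A reader might infer that cards are read 14 to 20 days late. That interval is the wait until the site receives them. The plan does not say who develops a card, when, or within what limit. A completed card could be one already developed at home, so there is no benchmark for lateness.

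A reader might infer that fading makes Day 14 look falsely clean by a known amount. The plan gives no stability figure. Assumed losses of 0 to 3% of positives per day would give 0 to 35% missed at Day 14 (1 − 0.97^14 = 0.347), but nothing in the documents supports any value in that range, and it includes no effect. The wait is the same in both arms, so it does not by itself favor one. Swabs go into stabilization buffer and tubes are frozen, so for stool the only issue shown is non-return.

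Nor can a loss of power be stated from the documents, because 9.1.1 gives no alpha, effect size or event rates.

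Finally, 6.3.3 uses the term in-person only for Days 7 and 28. Against that, a Day 14 physical exam with vital signs (6.6.4) and the weekly growth visits in 6.3.1.2 imply attendance on Day 14.

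What remains is the unused visit, the 14-to-20-day wait and the risk of non-return.

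**Conclusion.** The point holds as a cheap improvement of modest importance. Material from Days 8-14 reaches the site 14 to 20 days after collection although a visit falls on Day 14. The Day 14 card and stool of 0 to 10 infants are at risk of not being returned, about 5 of 45 (11%) in the even case. These counts rest on the planned 20% drop-out, on departing families returning nothing, and, for the figure of 5, on even timing. The comparability concern for Day 14 cards depends on the site developing them on receipt, and its size cannot be derived from the documents. A named secondary endpoint and a microbiome sampling day are affected. The primary comparison is not, and neither arm is favored by the wait.

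**What to change.** Add Day 14 in three places: 6.3.3.1, 6.3.3.4 and the stool-to-site row of Table 1. Families would bring all cards, swabs and frozen tubes collected since Day 7 to the existing Day 14 visit, and only later material on Day 28.

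The cost is one extra cold-pack transport and one extra sample receipt at a visit already scheduled. No new visit is needed, provided that Day 14 is attended in person, as the exam implies. The change does not help infants who leave between Day 7 and Day 14, and Day 21 material would still wait 7 days.

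A sentence in 6.3.3.4 saying who develops the cards and when would settle whether the storage question matters.

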6.3.3.5 Stool Sample Analysis

DNA and RNA will be extracted from stool swab samples and will be used for shotgun sequencing, next generation sequencing, and/or quantitative PCR to determine levels of *B. infantis*, total Bifidobacterium, microbial signatures, and relative abundance of the most abundant bacterial taxa. Biochemical analyses may be performed on stool chunk samples to evaluate markers as described in Section 6.3.2.

6.3.3.6 Stool Sample Retention by the Sponsor

[figure not shown]
Infant stool samples collected during the conduct of the study may be kept by the Sponsor for up to 10 years for use in future research. No personally identifiable information will be recorded on stool specimen tubes.

6.4 Study Procedures

All study procedures are listed in **Table 1: Schedule of Events** below.

Table 1: Schedule of Events

	Screening	Day 0 (Baseline)	Days 1-6	Day 7	Days 8-13	Day 14	Days 15-27	Day 28 (End of Study)
Diagnosis	x							
Consent	x							
Screening	x							
Study Visit	x	x		x		x		x
Physical exam		x		x		x		x
Supplementation			x	x	x	x		
Questionnaire		x	x	x	x	x	x	
Feeding log		x	x	x	x	x	x	
Stooling log		x	x	x	x	x	x	
Clinician symptom tool		x		x		x		x
Randomization		x						
Stool collection		x	x	x		x		x
Hemoccult test		x	x	x	x	x	x	x
Stool to site				x				x
AE reporting			x	x	x	x	x	x

6.4.1 Study Product Supplementation Period Days 1-14

- Daily oral administration of *B. infantis* INF108F or placebo

- Daily stool collection
- Questionnaires for Sleep, Feeding and Stool frequency and consistency

On or after Day 28, study staff will check-in with parents to make sure that the final stool samples have been collected and all remaining Questionnaires have been completed. Parents will bring all remaining frozen stool samples to the Day 28 in-person study visit.

6.4.2 AE Follow-up

Days 15-28

Parents will report any post-supplementation period adverse events experienced by their infant during this time.

6.4.3 Compliance

Compliance will be determined by treatment consumption, as reported in the Daily Log. Treatment compliance will be recorded as a percentage, calculated as the number of days of reported consumption divided by the number of days of treatment expected. Missed assessments will be recorded. For participants who are withdrawn prior to the end of the treatment period, percent adherence will be based on the number of days active in the study prior to withdrawal.

6.4.4 Double-Blind Placebo-Controlled Administration of INF108F and Placebo

Prior to start of oral administration of *B. infantis* INF108F or placebo, the participant will have a physical exam with vital signs.

6.5 Participant Completion and Withdrawal

6.5.1 Participant Completion

Participants will have completed the study upon completion of Day 28 AE follow-up period.

6.5.2 Participant Withdrawal

The parents may withdraw their infant from the study at any time by notifying the study team. Participants may be withdrawn from the study by the investigator if study procedures have not been followed or if the investigator determines the participant is not able to safely continue with the study due to an adverse event or other health-related issue. If 20 percent drop-out occurs, infants may be replaced to ensure adequate statistical power.

6.6 Data Management

6.6.1 Data Collection

Study data will be collected on paper Case Report Forms and entered by study staff into a RedCap database.

6.6.2 Access to Data

The PI, study coordinators, and CRAs (Study Monitors) will only have access to the blinded study data.

6.6.3 Stool Collection

Stool samples will be collected from the participants at the following time points:

- At Screening / Baseline
- Day 3 (within a window of Study Day 3-5)
- Day 14 (+/- 1 day)
- Day 28 (+/- 1 day)

The stool samples will be banked and used for 16s rRNA or metagenomic sequencing for microbiome evaluation and biologic studies.

6.6.4 Physical Examination

This will include measurement of vital signs, including weight, temperature, heart rate, and blood pressure, and physical examination including the skin, ears, nose and throat, abdomen, lungs, and heart.

7. RISKS AND DISCOMFORTS

7.1 Risks of Investigational Product(s) / Intervention(s)

Previous studies have shown that *B. infantis* INF108F is safe and well-tolerated by infants (both term and preterm) with no known side effects.

7.2 Risk of Study Procedures

7.2.1 Double-Blind, Randomized, Placebo-Controlled clinical trial Possible adverse events during the clinical trial include mainly GI symptoms (gas, abdominal distension, vomiting, diarrhea, constipation or abdominal pain).

7.2.2 Administration Procedure Minimal risk is associated with administration of *B. infantis* INF108F, including choking, spit up, and vomiting.

7.2.3 Stool collection All stool collection will be from fresh diapers, which does not impose any potential risk to the infants.

8. BENEFITS

8.1. Benefits of Investigational Product(s) / Intervention(s)

The risks associated with participation in this study are minimal in relation to the potential benefits derived by both the subject and society. Participants may derive two major benefits from the study. First, participants may have faster resolution of FPIAP. Second, participants may have modified gut microbiota which could potentially lead to reduced risk, or even prevention of, other allergic diseases in life.

Potential benefits to society include a better understanding of modulation of the infant gut microbiome and the associated clinical outcomes in infants with FPIAP.

8.2 Benefits of Study Procedure(s)

With the treatment of *B. infantis* INF108F, we anticipate that the infant's gut microbiome will likely be modified in a positive manner to correct the dysbiosis which leads to the development of FPIAP.

9. STATISTICAL ANALYSIS

9.1 SAMPLE SIZE CALCULATIONS AND STATISTICAL ANALYSIS PLAN

9.1.1 Determination of Sample Size

Approximately 100 infants and 100 mothers will be recruited and screened for the study to obtain a sample size of 50 participants for randomization, assuming a 50 percent screen fail rate. Forty (40) participants are expected to complete the study assuming a 20 percent drop-out rate. This sample size is based on a literature review of randomized clinical trials and the anticipated changes to the microbiome based on previous studies of *B. infantis*.

9.2 Data Analysis

9.2.1 General Considerations

Data will be collected and curated in a REDCap database [43] with support from the Human participants Core and exported into a suitable analysis format (e.g., STATA, SPSS, R analysis) for analysis. For continuous variables that

are normally distributed we will summarize them using mean with standard derivations and for those that are non-normally distributed, we will summarize with medians and inter-quartile ranges. For dichotomous data we will provide proportions. In addition to the baseline and outcome data, we will also summarize the recruitment numbers, those participants lost to follow-up, protocol violations and other relevant data.

9.2.2 Study Participant Populations

Randomization Approximately fifty (50) infants will be randomized in a 1:1 ratio to treatment probiotic or placebo. Randomization will occur immediately after all baseline period tasks have been confirmed to be completed and provide acceptable data.

Populations for Analyses The modified Intent to Treat (mITT) population will include all infants who are randomized and receive at least one supplementation. The Per Protocol (PP) population will include all randomized participants who do not have major protocol deviations. Major protocol deviations will be defined prior to unblinding of the data. Analysis on primary and secondary objectives will be completed based on the mITT population and the PP population; analysis on the exploratory objectives (perception of treatment) will be completed based on the mITT population.

Descriptive Statistics Descriptive statistics (mean, median, and standard deviation, minimum and maximum) of the quantitative variables will be summarized using number of subjects (n). The qualitative variables will be summarized using counts and percentages. All summaries will be presented by treatment group and time point (where relevant).

All CRF and laboratory data will be analyzed. Comparisons between treatment groups will be performed using Fisher's exact test or Pearson's Chi-Square test for categorical data and one-way ANOVA with Tukey's post hoc comparisons for individual timepoints or two-way repeated measures ANOVA for all timepoints for continuous data. Mean and standard deviations for certain groups and timepoints will be used as estimates in power calculations for future studies. Missing data will not be imputed in this study.

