5.4. Randomization and Study Supply Shipment

Randomization lists will be maintained in a secured area by the study team. If the randomization key is shared such that blinding is compromised, the Principal Investigator will be notified.

Randomization will occur immediately after all screening and baseline tasks have been confirmed to be completed and baseline data has been deemed acceptable. Baseline tasks include:

- Confirming infant/mother eligibility
- Obtaining informed consent
- Confirming baseline data collection
- Confirming baseline stool specimen collection.

Only infants for whom acceptable baseline data and stool samples have been collected will be randomized into the supplementation phase of the study. Using the randomization key generated by an unblinded statistician and held by an unblinded study site team member, eligible infants will be assigned a randomization code and randomized to a study product arm. The unblinded team member will provide the enrolled patient's parents with

the appropriate Study Product Kit in accordance with the randomization key. Infants will be randomized in a 1:1 ratio to the following arms:

- 8.0×10^9 CFU *B. infantis* INF108F
- Lactose placebo

After randomization, the study team will provide the assigned feeding kit to the participant. Study supplies that will be provided include:

- Feeding kits to include 14 sachets of study product (*B. infantis* INF108F or lactose placebo depending on randomization), oral syringes, and mixing cups
- Stool collection kits

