9.2.3 Efficacy Analysis

Primary Endpoint(s) The primary objective of the study is to assess the effectiveness of the probiotic, *B. infantis* INF108F, on modulating the gut microbiome composition of breastfed infants diagnosed with FPIAP from Baseline to Day 28, including colonization of INF108F. This will be measured using stool 16S analysis and quantitative PCR. Treatments will be compared using a Wilcoxon Rank Sum test.

Secondary Endpoint(s) The secondary objectives of this study as measured:

- Evaluating the reduction in stool frequency and improvement of stool consistency by Day 7 using Questionnaire
- Evaluating the improvement of infant GER symptoms by Day 14 using Questionnaire. Reduction by 50 percent from Baseline to Day 14 Infants with a reduction in the number of crying/fussing episodes of greater than or equal to 50 percent on Day 14 will be counted as a success. The number of successes per treatment group will be compared using a Chi-square or Fisher's Exact test, as appropriate.
- Evaluating the improvement of feeding difficulties by Day 14, using Questionnaire. The number of successes per treatment group will be compared using a Chi-square or Fisher's Exact test, as appropriate.

- Evaluating the improvement of infant's sleep by Day 14, using Questionnaire.
- Changes of stool cytokine profile by Day 28. The changes from baseline to Day 28 will be compared for the two groups using a repeated measures ANOVA.

Safety Analysis Fisher's Exact Test will also be used to compare treatment groups for SAEs and AEs resulting in withholding or discontinuing the study products. Adverse events will be summarized. Frequencies and percentages of subjects with treatment-emergent adverse events (TEAEs), serious TEAEs and TEAEs causing premature discontinuation will be provided by treatment group. An AE is treatment emergent if it 1) occurs after the first dose of randomized study treatment or 2) if it is present prior to receipt of randomized study treatment but worsens in severity or increases in frequency after the first dose of randomized study treatment.

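### Continuous outcomes other than the primary are compared without the baseline value as a covariate; ANCOVA on a suitable scale would be more precise at almost no cost

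*Combined protocol and SAP*

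**What the plan says.** Section 9.2.2 gives the general rule for comparing the arms on continuous data: "one-way ANOVA with Tukey's post hoc comparisons for individual timepoints or two-way repeated measures ANOVA for all timepoints for continuous data". Section 9.2.3 adds one specific rule, for stool cytokines: "The changes from baseline to Day 28 will be compared for the two groups using a repeated measures ANOVA". No section names a baseline covariate, ANCOVA or any other adjusted model.

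The baseline exists. Section 5.4 states: "Only infants for whom acceptable baseline data and stool samples have been collected will be randomized into the supplementation phase of the study". Section 6.3.3.1 requires the baseline stool to be taken before the first supplementation. Table 1 in section 6.4 schedules a stooling log, a questionnaire and a physical exam on Day 0.

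Section 9.2.2 also states: "Missing data will not be imputed in this study". On numbers, section 9.1.1 states: "Forty (40) participants are expected to complete the study assuming a 20 percent drop-out rate".

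Two parts of section 9.2.3 lie outside this point: the primary endpoint, compared by a Wilcoxon rank sum test, and the endpoints counted as successes and compared by Chi-square or Fisher's exact test.

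**The concern.** When a baseline value is available in randomized arms, an analysis can leave it out, subtract it, or adjust for it. Subtracting fixes the slope of follow-up on baseline at 1, while ANCOVA estimates the slope from the data. With only baseline and Day 28 in the model, the arm-by-time test of a repeated measures ANOVA is exactly the two-sample t-test on the change, so the cytokine rule is a change-score analysis.

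Which simple form is worse depends on r, the correlation between baseline and follow-up. Below 0.5 the change score is the less precise; above 0.5 the unadjusted follow-up comparison is. The documents give no r, so the better form cannot be chosen in advance. ANCOVA removes that choice. With about 40 completers, the loss affects the width of the intervals and the chance of detecting a moderate effect on stool markers and stool frequency.

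**Working it through.** **The plan's own figures.** 100 screened × 0.5 = 50 randomized; 50 × 0.8 = 40 completers; 40 / 0.8 = 50. The recruitment arithmetic reproduces. Section 9.1.1 states no effect size, SD, alpha or power, so there is no power figure to reproduce.

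**Inputs.** From the documents: 50 randomized 1:1 and 40 completers, hence 20 per arm. Assumed: two-sided 5% level, SD 1 at both times, r from 0.3 to 0.7, a true difference of 0.8 SD, and data roughly normal on the analysis scale.

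**Variance of the arm difference**, relative to an unadjusted comparison of follow-up values:
- unadjusted: 1
- change from baseline: 2(1 − r)
- ANCOVA: 1 − r², times 1 + 1/(N − 4) for estimating the slope. With N = 40 this factor is 1 + 1/36 = 1.028.

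Without that factor, ANCOVA over change is (1 + r)/2 = 0.65, 0.75, 0.85 at r = 0.3, 0.5, 0.7, and ANCOVA over unadjusted is 1 − r² = 0.91, 0.75, 0.51.

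**Power** (noncentral t). The unadjusted noncentrality is 0.8 / √(2/20) = 2.530 on 38 df. For the other forms, divide by the square root of the relative variance; ANCOVA has 37 df.

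| r | Unadjusted follow-up | Change | ANCOVA |
|---|---|---|---|
| 0 | 69% | 41% | 68% |
| 0.3 | 69% | 55% | 72% |
| 0.5 | 69% | 69% | 80% |
| 0.7 | 69% | 89% | 93% |

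Example at r = 0.5: the ANCOVA relative variance is 0.75 × 1.028 = 0.771, its root is 0.878, the noncentrality is 2.530 / 0.878 = 2.88, and power is 80%.

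**Standard errors with drop-out.** Simulation with 25 per arm, 10 drop-outs, a further 5% or 10% of samples missing at random and equal correlation between visits (4,000 runs per cell) gave these Day 28 standard errors, in SD units:

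| r | Missing | ANCOVA | Change | Unadjusted | ANCOVA vs change | ANCOVA vs unadjusted |
|---|---|---|---|---|---|---|
| 0.3 | 5% | 0.315 | 0.391 | 0.324 | −19.4% | −2.7% |
| 0.3 | 10% | 0.328 | 0.400 | 0.338 | −17.9% | −2.8% |
| 0.5 | 5% | 0.286 | 0.324 | 0.329 | −11.8% | −13.1% |
| 0.5 | 10% | 0.299 | 0.341 | 0.335 | −12.5% | −10.9% |
| 0.7 | 5% | 0.233 | 0.246 | 0.326 | −5.4% | −28.5% |
| 0.7 | 10% | 0.248 | 0.263 | 0.341 | −5.8% | −27.3% |

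The type I error of ANCOVA was 0.047-0.058. A mixed model given the true covariance improved on ANCOVA by only 0.6-2.4%.

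**Equivalence.** In 200 simulated two-visit data sets, the arm-by-time F and the squared t on change differed by at most 1.4e-14.

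**Tukey.** At 38 df with two arms, the Tukey and t critical values are both 2.0244, so the post hoc step changes nothing.

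**Scale.** Simulated lognormal markers (log-SD 1, 0.8 SD effect on the log scale, 20 per arm), analysed by ANCOVA without transformation, gave power of about 51 / 58 / 69% at r = 0.3 / 0.5 / 0.7. An unadjusted t-test on the logs gave about 70%. The 72 / 80 / 93% in the first table is reached only on the log scale for such markers.

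**The case against.** The strongest reply is that this is a preference about efficiency. The planned tests hold their type I error, the outcomes are secondary or exploratory, and section 9.1.1 promises no power for them. All of that is true and sets the weight of the point. It does not remove it: the baseline is already collected, and in the range tried ANCOVA was at least as powerful as both planned forms from r = 0.2 up and lost about one point at most below that.

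Second, a reader might infer that the plan ignores baseline throughout. The documents do not support that. The cytokine rule uses change from baseline, section 3.1.2 words stool frequency and the other symptoms as changes, and section 9.2.2 does not say whether its one-way ANOVA is run on raw values or on changes. The firm comparison is therefore with the change analysis.

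Third, the gain may be small. At r = 0.3 it is only 3 points of power over an unadjusted comparison, and break-even against that form is at r of about 0.16. Section 1.1 describes rapid change in the infant microbiota, so a low r is possible for stool markers. This stands. Against the change score, however, a low r makes the gain larger.

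Fourth, scale can matter more than the covariate. For the simulated lognormal markers at r up to 0.5, moving to logs gained more than adding the covariate. This stands, and the fix has to specify the scale.

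**Conclusion.** The point holds as a free improvement in precision. Adjusting for baseline lowers the Day 28 standard error by about 5-19% against the change analysis in section 9.2.3. Against the one-way ANOVA in section 9.2.2 the reduction is about 3-29%, but only if that ANOVA is run on raw follow-up values. These sizes rest on an assumed r of 0.3 to 0.7, roughly normal data on the analysis scale, and data missing completely at random.

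A reader might go further and conclude that the planned analyses are biased or invalid. They are not: type I error was about 5% for the unadjusted, change and ANCOVA forms alike. Nor does this point establish a multiplicity problem across visits or a particular loss of infants from an all-visits ANOVA. Those are separate questions, and the second depends on a sampling schedule that section 6.6.3 gives as a few time points and sections 6.3.2.1 and 6.4.1 describe as daily.

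**What to change.** In section 9.2.2, and in the cytokine rule of section 9.2.3, replace the ANOVA rules with:

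> Arms will be compared at the named visit by ANCOVA adjusting for the baseline value of the outcome, in all mITT infants observed at that visit. Right-skewed measures (for example stool cytokines and calprotectin) will be log-transformed at both baseline and follow-up, with the scale fixed before unblinding.

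Where several visits are analysed together, use a likelihood-based mixed model with baseline, arm, visit and arm-by-visit. It keeps partly observed infants, so the no-imputation sentence can stay. Delete the Tukey step.

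Apply this to the stool markers and stool frequency. Apply it to sleep only if the Day 0 questionnaire covers sleep: Table 1 lists a questionnaire on Day 0, but section 6.3.1.2 lists the sleep questionnaire from Day 7 only. The wording needs one named visit per outcome. Section 9.2.3 gives Day 28 for cytokines and Day 14 for sleep. For stool frequency, section 9.2.3 ("Evaluating the reduction in stool frequency and improvement of stool consistency by Day 7 using Questionnaire") and section 3.1.2 ("Changes to stool frequency by Study Day 7, 14 and 28") must first be reconciled.

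Cost: wording only, with no added samples or visits, and the software named in section 9.2.1 fits these models. The downsides are one degree of freedom, a missing-at-random assumption for the mixed model, and possibly an amendment with IRB review under section 9.4. The change is best made before the interim analysis in section 9.3.
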